8.2 Secondary objective(s)

There are descriptive and comparative secondary objectives in this study. The secondary objectives are grouped by type of analysis (rates, comparative, interaction) and outcome (uterine perforation, IUD expulsion, indicators of difficult insertion).

Rates: uterine perforation

3. To estimate the incidence rate and cumulative incidence of uterine perforation among women using IUDs
4. To estimate the incidence rate and cumulative incidence of uterine perforation among women using IUDs for the following categories:
 - ≤ 6 weeks postpartum
 - > 6 weeks and ≤ 14 weeks postpartum
 - > 14 weeks and ≤ 52 weeks postpartum
 - > 52 weeks postpartum, including women without recorded delivery within the past 52 weeks
 - ≤ 14 weeks postpartum

- > 14 weeks postpartum, including women without recorded delivery within the past 52 weeks
 - ≤ 36 weeks postpartum
 - > 36 weeks postpartum, including women without recorded delivery within the past 52 weeks
5. To estimate the incidence rate and cumulative incidence of uterine perforation among women who were and were not breastfeeding at the time of IUD insertion
 6. To estimate the incidence rate and cumulative incidence of uterine perforation among women with different types of IUD (i.e., LNG-IUD and copper IUD)
 7. To estimate the incidence rate and cumulative incidence of uterine perforation among women with and without menorrhagia in the 12 months before IUD insertion

Rates: IUD expulsion

8. To estimate the incidence rate and cumulative incidence of IUD expulsion among users of IUDs
9. To estimate the incidence rate and cumulative incidence of IUD expulsion among users of IUDs for the following categories:
 - ≤ 6 weeks postpartum
 - > 6 weeks and ≤ 14 weeks postpartum
 - > 14 weeks and ≤ 52 weeks postpartum
 - > 52 weeks postpartum, including women without recorded delivery within the past 52 weeks
 - ≤ 14 weeks postpartum
 - > 14 weeks postpartum, including women without recorded delivery within the past 52 weeks
 - ≤ 36 weeks postpartum
 - > 36 weeks postpartum, including women without recorded delivery within the past 52 weeks
10. To estimate the incidence rate and cumulative incidence of IUD expulsion among women who were and were not breastfeeding at the time of IUD insertion
11. To estimate the incidence rate and cumulative incidence of IUD expulsion among women with different types of IUD (i.e., LNG-IUD and copper IUD)

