9.3.3 Outcome measures

- **Person-time at risk** will be calculated from the IUD insertion date until the first occurrence of any of the following: uterine perforation, IUD expulsion, or censoring date.
- **Date uterine perforation confirmed** is the date on which uterine perforation is documented. This may be complete perforation, with IUD migration into the pelvis or abdominal cavity, or partial perforation (i.e., incomplete, with IUD embedded in the myometrium). Cases of both partial and complete perforation will be considered under the umbrella term “perforation.” Cases will be classified as yes, no, or undetermined perforation.
- **Date IUD expulsion confirmed** is the date on which IUD expulsion is documented. IUD expulsion, which is the unintended, spontaneous expulsion of the IUD, will be determined from the EHR, including clinical notes, using algorithms developed during the validation study. Both partial and complete expulsions will be considered under the umbrella term “expulsion.” Cases will be classified as yes, no, or undetermined expulsion.

If both perforation and expulsion (e.g., complete or partial perforation of the *vagina or cervix* by the IUD) occurred and were documented on the same date, then the outcome will be classified as both perforation and IUD expulsion, since these outcomes are evaluated separately throughout this study. If both perforation and IUD expulsion occurred for the same IUD insertion but on different dates, then the earlier date will constitute a stopping date for assessment of all objectives. No analysis will be conducted to assess both perforation and IUD expulsion as a composite outcome or as a subgroup analysis among those with both outcomes.

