9.7.1.2 Crude incidence rates and crude cumulative incidence

9.7.1.2.1 Crude incidence rates

While the main study analyses will account for the anticipated underlying change in risk of outcomes across the time women are exposed to inserted IUDs, constant incidence rates will also be calculated across the person-time women contribute to the study. Following characterization of variables, person-time at risk and crude incidence rates of outcomes will be calculated. Crude incidence rates will be assessed rather than incidence proportions, since patients will contribute variable time at risk to the study. Crude incidence rates will be calculated for all study cohorts and within levels of exposure variables.

Crude incidence rates will be calculated as the number of outcomes occurring during the person-time at risk divided by the total person-time at risk (in person-years). Crude incidence rates will be reported as point estimates (number of cases per 1,000 person-years) and 95% CIs.

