9.7.1.2.2 Crude cumulative incidence

Crude estimates of the cumulative incidence, defined as number of outcomes occurring up to a timepoint out of the number of IUD insertions, will be estimated using the Kaplan-Meier method. The corresponding curve over time, also known as the failure function (i.e., 1-survival function), will be plotted. Crude cumulative incidence will be estimated and plotted for all study cohorts and within levels of exposure variables.

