3.7 Start and Stop Dates¹

- *IUD insertion date* is the date on which IUD insertion is documented
- *Beginning date of study period*: the first date EHR data are available from the data source for this study (KPNC, KPSC, and KPWA) or the date when Mirena was launched (RI)
- *End date of study period*: the last date on which EHR data are available from the data source for this study
- *Date of start of enrollment* (KPNC, KPSC, and KPWA only) is the earliest date of enrollment in the database for the woman (will be used to calculate look-back period)
- *Date of first clinical encounter* (RI only) is the earliest in-person visit in the database for the woman (will be used to calculate look-back period)
- *Date of disenrollment from the database* (KPNC, KPSC, and KPWA only) is the date, after the index date, on which the woman was no longer enrolled in an eligible insurance plan (one gap of ≤ 31 days per year will be allowed)
- *Date of last clinical encounter in database* (RI only) is the last date on which a woman had an in-person encounter that was recorded in the database

¹ Note that the actual dates will remain at each data source research partner. The dates may be offset for each patient as an additional data protection measure before transfer of data to RTI-HS.

- *Censoring date* is the earliest of the following dates: date of removal of IUD, date of a subsequent IUD reinsertion, date of start of new pregnancy, hysterectomy date, date of bilateral oophorectomy or other type of sterilization, expiration of IUD, death date, date of disenrollment from database (KPNC, KPSC, and KPWA only) or last clinical encounter (RI only), and end date of study period

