4.1.3 Crude Cumulative Incidence

Crude estimates of the cumulative incidence, defined as the number of incident outcomes occurring up to a time point out of the number of IUD insertions, will be estimated using the Kaplan-Meier method.

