Programming note 1: The list of variables will be adjusted after reviewing the data.

Table Layout 8. Crude Incidence Rates and Cumulative Incidence for Uterine Perforation;
Analysis Set: Complete Study Population, First IUD Insertion;
Database: Pooled

Groups	Insertions	Person-years	Events	Crude Incidence Rate ^a (95% CI)	1-Year Crude Cumulative Incidence ^b (95% CI)	5-Year Crude Cumulative Incidence ^b (95% CI)
Analysis set						
Complete study population	xxx	xxx.x	xx	x.xx (x.xx, x.xx)	xx.x% (xx.x%, xx.x%)	xx.x% (xx.x%, xx.x%)
Breastfeeding status available	xxx	xxx.x	xx	x.xx (x.xx, x.xx)	xx.x% (xx.x%, xx.x%)	xx.x% (xx.x%, xx.x%)
IUD type available	xxx	xxx.x	xx	x.xx (x.xx, x.xx)	xx.x% (xx.x%, xx.x%)	xx.x% (xx.x%, xx.x%)
Postpartum status						
6 weeks or less	xxx	xxx.x	xx	x.xx (x.xx, x.xx)	xx.x% (xx.x%, xx.x%)	xx.x% (xx.x%, xx.x%)
> 6 to ≤ 14 weeks	xxx	xxx.x	xx	x.xx (x.xx, x.xx)	xx.x% (xx.x%, xx.x%)	xx.x% (xx.x%, xx.x%)
> 14 to ≤ 52 weeks	xxx	xxx.x	xx	x.xx (x.xx, x.xx)	xx.x% (xx.x%, xx.x%)	xx.x% (xx.x%, xx.x%)
> 52 weeks or no delivery	xxx	xxx.x	xx	x.xx (x.xx, x.xx)	xx.x% (xx.x%, xx.x%)	xx.x% (xx.x%, xx.x%)
≤ 14 weeks	xxx	xxx.x	xx	x.xx (x.xx, x.xx)	xx.x% (xx.x%, xx.x%)	xx.x% (xx.x%, xx.x%)
> 14 weeks or no delivery	xxx	xxx.x	xx	x.xx (x.xx, x.xx)	xx.x% (xx.x%, xx.x%)	xx.x% (xx.x%, xx.x%)
≤ 36 weeks	xxx	xxx.x	xx	x.xx (x.xx, x.xx)	xx.x% (xx.x%, xx.x%)	xx.x% (xx.x%, xx.x%)
> 36 weeks or no delivery	xxx	xxx.x	xx	x.xx (x.xx, x.xx)	xx.x% (xx.x%, xx.x%)	xx.x% (xx.x%, xx.x%)
Breastfeeding status						
Yes	xxx	xxx.x	xx	x.xx (x.xx, x.xx)	xx.x% (xx.x%, xx.x%)	xx.x% (xx.x%, xx.x%)
No	xxx	xxx.x	xx	x.xx (x.xx, x.xx)	xx.x% (xx.x%, xx.x%)	xx.x% (xx.x%, xx.x%)
Undetermined	xxx	xxx.x	xx	x.xx (x.xx, x.xx)	xx.x% (xx.x%, xx.x%)	xx.x% (xx.x%, xx.x%)
IUD type						
LNG-IUD	xxx	xxx.x	xx	x.xx (x.xx, x.xx)	xx.x% (xx.x%, xx.x%)	xx.x% (xx.x%, xx.x%)
Copper IUD	xxx	xxx.x	xx	x.xx (x.xx, x.xx)	xx.x% (xx.x%, xx.x%)	xx.x% (xx.x%, xx.x%)
Unknown	xxx	xxx.x	xx	x.xx (x.xx, x.xx)	xx.x% (xx.x%, xx.x%)	xx.x% (xx.x%, xx.x%)

Groups	Insertions	Person-years	Events	Crude Incidence Rate ^a (95% CI)	1-Year Crude Cumulative Incidence ^b (95% CI)	5-Year Crude Cumulative Incidence ^b (95% CI)
Menorrhagia						
Yes	xxx	xxx.x	xx	x.xx (x.xx, x.xx)	xx.x% (xx.x%, xx.x%)	xx.x% (xx.x%, xx.x%)
No	xxx	xxx.x	xx	x.xx (x.xx, x.xx)	xx.x% (xx.x%, xx.x%)	xx.x% (xx.x%, xx.x%)

CI = confidence interval; IUD = intrauterine device; LNG-IUD = levonorgestrel-releasing intrauterine system.

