^a Incidence rates are expressed per 1,000 person-years.

^b Crude estimate of cumulative incidence, defined as the number of incident outcomes occurring during a specific time period out of the number of IUD insertions during the same time period, were estimated using the Kaplan-Meier method.

Generated using xxxx.sas on xxxxxxxx.

Programming note 1: Summary for IUD type available set and ty IUD type will only be presented in the pooled table, not by site.

**Table Layout 9. Prevalence of Difficult IUD Insertion by Exposure Group and Outcome;
 Analysis Set: Complete Study Population, First IUD Insertion;
 Database: Pooled**

Exposure or Outcome Group		N	Cervical Dilation n (%)	Ultrasound Guidance n (%)	Paracervical Block n (%)	Provider Note n (%)	Use of Misoprostol n (%)	Any n (%)
All patients		xx	xx (xx.x)	xx (xx.x)	xx (xx.x)	xx (xx.x)	xx (xx.x)	xx (xx.x)
Breastfeeding	Yes	xx	xx (xx.x)	xx (xx.x)	xx (xx.x)	xx (xx.x)	xx (xx.x)	xx (xx.x)
	No	xx	xx (xx.x)	xx (xx.x)	xx (xx.x)	xx (xx.x)	xx (xx.x)	xx (xx.x)
	Undetermined	xx	xx (xx.x)	xx (xx.x)	xx (xx.x)	xx (xx.x)	xx (xx.x)	xx (xx.x)
Postpartum status	6 weeks or less	xx	xx (xx.x)	xx (xx.x)	xx (xx.x)	xx (xx.x)	xx (xx.x)	xx (xx.x)
	> 6 to ≤ 14 weeks	xx	xx (xx.x)	xx (xx.x)	xx (xx.x)	xx (xx.x)	xx (xx.x)	xx (xx.x)
	> 14 to ≤ 52 weeks	xx	xx (xx.x)	xx (xx.x)	xx (xx.x)	xx (xx.x)	xx (xx.x)	xx (xx.x)
	> 52 weeks or no delivery	xx	xx (xx.x)	xx (xx.x)	xx (xx.x)	xx (xx.x)	xx (xx.x)	xx (xx.x)
IUD type	LNG-IUD	xx	xx (xx.x)	xx (xx.x)	xx (xx.x)	xx (xx.x)	xx (xx.x)	xx (xx.x)
	Copper IUD	xx	xx (xx.x)	xx (xx.x)	xx (xx.x)	xx (xx.x)	xx (xx.x)	xx (xx.x)
	Undetermined	xx	xx (xx.x)	xx (xx.x)	xx (xx.x)	xx (xx.x)	xx (xx.x)	xx (xx.x)
Menorrhagia	Yes	xx	xx (xx.x)	xx (xx.x)	xx (xx.x)	xx (xx.x)	xx (xx.x)	xx (xx.x)
	No	xx	xx (xx.x)	xx (xx.x)	xx (xx.x)	xx (xx.x)	xx (xx.x)	xx (xx.x)
IUD expulsion	Yes	xx	xx (xx.x)	xx (xx.x)	xx (xx.x)	xx (xx.x)	xx (xx.x)	xx (xx.x)
	No	xx	xx (xx.x)	xx (xx.x)	xx (xx.x)	xx (xx.x)	xx (xx.x)	xx (xx.x)
Uterine perforation	Yes	xx	xx (xx.x)	xx (xx.x)	xx (xx.x)	xx (xx.x)	xx (xx.x)	xx (xx.x)
	No	xx	xx (xx.x)	xx (xx.x)	xx (xx.x)	xx (xx.x)	xx (xx.x)	xx (xx.x)

IUD = intrauterine device; LNG-IUD = levonorgestrel-releasing intrauterine system.

Generated using xxxx.sas on xxxxxxx.

Programming note 1: Results by IUD type will be presented only for the pooled table, not by site.

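### Crude cumulative incidence is defined per IUD insertion but estimated as 1 minus Kaplan-Meier, which is risk while the device stays in place; the label should match the estimator (minor)

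*Protocol*

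**What the plan says.** Three places define the same quantity.

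- Protocol 9.7.1.2.2: cumulative incidence is "defined as number of outcomes occurring up to a timepoint out of the number of IUD insertions, will be estimated using the Kaplan-Meier method". The section then plots the failure function, one minus survival.
- SAP 4.1.3: "defined as the number of incident outcomes occurring up to a time point out of the number of IUD insertions", again by Kaplan-Meier.
- SAP 9.5, Table Layout 8, footnote b, which would be printed under the results: "out of the number of IUD insertions during the same time period, were estimated using the Kaplan-Meier method". This adds a qualifier to the denominator that the other two lack.

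The stopping rules are elsewhere. SAP 3.7 sets the censoring date as "the earliest of the following dates: date of removal of IUD, date of a subsequent IUD reinsertion, date of start of new pregnancy", and continues with hysterectomy, sterilization, device expiry, death, disenrollment or last encounter, and study end. If perforation and expulsion occur on different dates, Protocol 9.3.3 says "then the earlier date will constitute a stopping date for assessment of all objectives". Under SAP Table 1, the indicator for the outcome under study stays at 0 when follow-up ends for any of these reasons.

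The figures serve secondary objectives 3-12. Objective 3, for example, is "To estimate the incidence rate and cumulative incidence of uterine perforation among women using IUDs". SAP 6.2.2.1 reports them at years 1 and 5, overall and by exposure group. Neither document mentions competing risks.

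**The concern.** A proportion of insertions and a Kaplan-Meier failure probability agree only if nothing but administrative censoring can end follow-up before the outcome. Here most of the listed stops are not administrative: once the device is out, expelled or expired, or the woman is pregnant or has died, the plan's time at risk for that insertion is over. Kaplan-Meier treats these women as if they stayed at risk at the same hazard as those still under observation. The result is the risk that would apply if the device remained in place.

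That is a legitimate quantity, but it is not what the footnote says is being reported. A reader who takes the footnote at its word would read "5-Year Crude Cumulative Incidence" as the fraction of insertions with the outcome by 5 years, and that reading is too high. The invitation is real: Protocol 9.5 quotes the earlier European study per 1,000 insertions, and Protocol 9.9 plans to set the incidence rates against the literature.

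**Working it through.** **The plan's own figures.** No cumulative incidence is planned, so there is none to reproduce. The nearest stated figures do reproduce. The reference risk is 81/61,448 = 1.32 per 1,000 (stated 1.3). For primary objective 1, expected events are 60,000 × 0.0013 = 78, and power at HR 2.0 with 60:40 allocation is Φ(√(78 × 0.6 × 0.4) × ln 2 − 1.96) = Φ(1.04) = 85% (stated 85%). Nothing in that calculation depends on how cumulative incidence is estimated.

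**Formulas.** Let h(t) be the outcome hazard, H(t) its integral, and λ a constant competing hazard for all non-administrative stops.

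- 1−KM at t: 1 − exp(−H(t)).
- Share of insertions with the outcome, competing stops allowed for: ∫₀ᵗ h(u)·exp(−H(u) − λu) du.
- λ = −ln(1 − loss)/5, where loss is the competing loss by year 5.

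The second expression is smaller whenever λ > 0.

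**Inputs.** From the documents: 1−KM for perforation at 1 year set to 1.3 per 1,000 (Protocol 9.5). Assumed, because the documents give no value: competing loss of 30-60% by year 5, and 20% (flat hazard), 40%, 60% or 80% of H(5) falling in year 1.

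**Perforation, 1 year.** The year-1 hazard is −ln(1 − 0.0013) = 0.001301. With 60% loss, λ = −ln(0.4)/5 = 0.183 and the share is 0.001301/0.1846 × (1 − exp(−0.1846)) = 1.19 per 1,000. The ratio is 1.30/1.19 = 1.09. With 30% loss (λ = 0.071) the share is 1.25 and the ratio 1.04.

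**Perforation, 5 years, per 1,000.**

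| Hazard in year 1 | 1−KM | Share, 30% loss | Share, 60% loss | Ratios |
|---|---|---|---|---|
| 20% (flat) | 6.48 | 5.45 | 4.25 | 1.19, 1.53 |
| 40% | 3.25 | 2.83 | 2.34 | 1.15, 1.39 |
| 60% | 2.17 | 1.96 | 1.70 | 1.11, 1.28 |
| 80% | 1.62 | 1.52 | 1.38 | 1.07, 1.18 |

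Layout 8 prints percentages to one decimal. At 1 year both quantities print as 0.1%. The gap of 4-9% is also smaller than the sampling error: 225,000 × 0.0013 = 292 events, and 1.96/√292 is about 11%. At 5 years the printed difference is between nil and 0.2 percentage points.

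**Expulsion, 5 years.** With an assumed 1−KM of 5%, the share is 4.2-4.7% at 30% loss and 3.3-4.3% at 60% loss, the lower end of each being the flat hazard. That would show in the table.

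**Sensitivity to the assumptions.** Let λ run from 0.05 to 0.30 per year, which is 1 − exp(−5λ) = 22-78% loss by year 5. The 5-year excess is then 13-93% for a flat hazard, and 9-54% if the hazard in years 2-5 is one quarter of that in year 1. The illustrative range is therefore not a bound.

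**Three quantities, not two.** Take a flat perforation hazard, λ = 0.15 and administrative loss of 0.15 per year. At 5 years the raw proportion of insertions with an observed outcome is 3.36 per 1,000, the cumulative incidence with competing events is 4.56, and 1−KM is 6.48.

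**The case against.** The best defence is that the analysis is fully specified and only a gloss is loose. Kaplan-Meier is named, the plot is one minus survival, time at risk ends when the device is no longer in place, and the objectives speak of women using IUDs. Protocol 9.7.1.2.1 adds "Crude incidence rates will be assessed rather than incidence proportions, since patients will contribute variable time at risk to the study", which also sits badly with a proportion of insertions. No programmer would compute anything else. This largely stands: the documents mostly point to risk while the device is in place. A reader might infer that the intended quantity cannot be told at all, or that Kaplan-Meier is the wrong method; the texts support neither. What remains is that the same incorrect denominator is written in three places, one of them a footnote to the results.

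The sizes also rest wholly on assumed loss and hazard shapes, including the 5% expulsion risk. That is correct. Direction is certain wherever competing stops precede the outcome; magnitude is not.

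Finally, an Aalen-Johansen estimate does not deliver the written definition either, because disenrollment and study end are still censored. That is also correct, and it is why relabelling comes first and the extra estimator is optional.

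**Conclusion.** The point holds as a mismatch between label and estimator. As written, the reported cumulative incidence is larger than the quantity its definition names whenever a removal, reinsertion, other outcome or similar stop comes before the outcome. The gap is small at 1 year and larger at 5 years, and it matters mainly for expulsion. Its true size is unknown, because the documents supply no removal rate, expulsion risk, 5-year risk or hazard shape.

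A reader might go further and infer that the primary results are biased by ignored competing risks. The documents do not support that. The primary analyses are Cox hazard ratios, which keep their cause-specific meaning when competing stops are censored. Objectives 17 and 25 use person-time rates, and Table 4 power is unaffected. Only the descriptive figures and curves of objectives 3-12 need a different reading. The weight is minor.

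**What to change.** **Recommended.** In Protocol 9.7.1.2.2, SAP 4.1.3 and Layout 8 footnote b, keep 1−KM. Delete the phrase that makes the number of IUD insertions the denominator, and in footnote b its same-period qualifier too. Define the figure instead as *risk while the IUD remains in place, assuming independent censoring*. The cost is wording in three places, with no new data or programming.

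**Optional.** If a per-insertion risk is wanted for comparison with per-insertion figures elsewhere, add the Aalen-Johansen cumulative incidence at 1 and 5 years. Treat all non-administrative stops, including the other outcome, as competing events, and disenrollment, last encounter (RI) and study end as censoring. A perforation and expulsion on the same date remains an event in each analysis, as Protocol 9.3.3 provides. Call the result cumulative incidence in the presence of competing events, not the raw proportion of insertions.

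This costs one further estimator. A reader might assume it needs a new stop-reason code from the sites. It does not for this split: SAP 3.7 lists disenrollment, last-encounter and study-end dates separately, and SAP 4.1 says sites supply the Section 3 variables. The class can therefore be derived by comparing dates, except for same-day ties. A finer split of the competing events would need a code.

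The added 5-year risks would be lower than 1−KM. A note should say that groups with equal hazards but different removal will differ on this measure: at 30% versus 60% loss, the 5-year ratio is 1.10 (1.52/1.38, 80% of hazard in year 1) to 1.28 (5.45/4.25, flat). The Cox models, rates, IRR and IRD stay as they are.

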9.7.1.3 Crude and adjusted hazard ratios

9.7.1.3.1 Crude hazard ratios

In binary comparisons, crude hazard ratios will be estimated for the exposed group (e.g., breastfeeding at the time of IUD insertion) relative to the referent group (e.g., not breastfeeding at the time of IUD insertion) using Cox regression models. In categorical comparisons, crude hazard ratios will be estimated for each exposure group (e.g., IUD insertion ≤ 6 weeks postpartum) relative to the referent group (IUD insertion > 52 weeks postpartum) using Cox regression models. These crude hazard ratios will be calculated for each outcome without adjustment for covariates. All crude hazard ratios will be reported as point estimates with 95% CIs.

The proportional hazards assumption between each exposure and outcome pairing will be assessed using visual examination of hazard functions, log-log survival curves, and goodness-of-fit testing

using Schoenfeld residuals (Kleinbaum and Klein, 2012). For violations of the proportional hazards assumption, time-dependent exposure covariates will be included in crude and adjusted hazard ratio models by fitting interaction terms with continuous or categorical time. Additional details are included in the statistical analysis plan.

9.7.1.3.2 Control for confounding effects

Confounding will be controlled through the use of propensity scores, based on the values of covariates at the time of IUD insertion. Propensity scores estimate the probability that a given patient will be exposed conditional on measured covariates and can serve as a summary confounder variable. Propensity scores can perform better than conventional regression methods when the number of events relative to the number of potential confounders is small, because rather than having to model the events with many variables, which may lead to overfitting of the outcome model, one can instead model the exposure, for which the larger number of exposed people provides sufficient data to accommodate a rich model (Cepeda et al., 2003). This advantage may be important in this study, given the low number of expected events, particularly for uterine perforation, within this study.

Separate propensity score models will be developed for exposure-outcome pairings related to the primary objectives, IUD type, and menorrhagia. Additionally, separate propensity score models will be developed for assessment of first observed IUD insertions and for assessment of subsequent IUD insertions. Thus, 16 propensity score models will be developed to assess exposures: 8 for models including first observed IUD insertions and 8 for models including subsequent IUD insertions (Table 6). One propensity score model will also be developed to assess the interaction between breastfeeding and early versus late postpartum IUD insertion. This will yield a total of 17 propensity score models for this study.

Table 6. Propensity score models for postmarketing requirement study defined by exposure and outcomes of interest

Model number	Exposure (dependent variable of propensity score model)	Outcome (not included in propensity score model)
1 (primary objective)	Breastfeeding status (yes vs. no)	Uterine perforation
2 (primary objective)	Postpartum insertion (4 categories) ^a	Uterine perforation
3	IUD type (LNG vs. copper)	Uterine perforation
4	Menorrhagia (yes vs. no)	Uterine perforation
5	Breastfeeding status	IUD expulsion
6	Postpartum insertion (4 categories) ^a	IUD expulsion
7	IUD type (LNG vs. copper)	IUD expulsion
8	Menorrhagia (yes vs. no)	IUD expulsion
9	Interaction of breastfeeding and early vs. late postpartum (breastfeeding/ \leq 14 weeks; breastfeeding/ $>$ 14 weeks; no breastfeeding/ \leq 14 weeks; no breastfeeding/ $>$ 14 weeks [referent])	Uterine perforation

^a Secondary objectives include dichotomization of “early” and “late” postpartum categories. Separate propensity score models will not be *developed* for these objectives. Rather, the propensity scores calculated with the four-category variable will be used, and the distribution of scores will be collapsed into the categories for each secondary objective. Assessment of distributions of propensity scores will be performed within these collapsed categories.

Propensity scores for dichotomous exposure variables will be estimated by fitting a logistic regression model that incorporates data source (i.e., KPNC, KPSC, KPWA, or RI) and measured potential predictors of exposure as independent variables (all baseline variables in Section 9.3.1 will be considered). The dependent variable in the propensity score model is exposure status (e.g., women breastfeeding at the time of IUD insertion vs. not breastfeeding at the time of IUD insertion).

Propensity scores for the categorical variable (i.e., timing of postpartum insertion) will be estimated by fitting a multinomial logistic regression model that incorporates data source (i.e., KPNC, KPSC, KPWA, or RI) and measured potential predictors of exposure as independent variables (all baseline variables in Section 9.3.1 will be considered). The dependent variable in the propensity score model is exposure category (i.e., ≤ 6 weeks postpartum; > 6 and ≤ 14 weeks postpartum; > 14 and ≤ 52 weeks postpartum; > 52 weeks postpartum [referent]).

Covariates will be assessed for inclusion in propensity score models based on association with the study outcome (Brookhart et al., 2006) and thus will not be outcome blinded. Categorical variables will be assessed for inclusion based on indicator coding of the categories. Continuous variables (including integer count variables) will be assessed for inclusion as continuous, dichotomous, and categorical (i.e., indicator coded) variables, as appropriate. Covariates will be included in the propensity score model if the crude hazard ratio is greater than 1.11 or less than 0.90. Additional confounders will be selected for inclusion within propensity score models if a 10% change in the hazard ratio of the *exposure*-outcome relationship occurs when adjusting for that variable, including a 10% change in any level of a categorical exposure variable.

From the fitted logistic regression models, propensity scores will be estimated for each IUD insertion. The distribution of propensity scores among categories (e.g., breastfeeding at the time of IUD insertion versus not breastfeeding at the time of IUD insertion) will be examined.

The propensity scores will be used to calculate weights for each IUD insertion within each exposure group. The weights will be the “overlap weights” and will use data from the IUD insertions included in the propensity score models after reweighting (Li et al., 2018).^{*} To assess whether covariates are balanced across exposure groups after weighting, the distribution of each variable will be compared between categories of the exposure variable, and balance parameters (e.g., standardized differences) (Austin and Stuart, 2015) will be calculated. Pairwise balance parameters (e.g., pairwise standardized differences) will be used for the categorical exposure variable (postpartum timing) in which each category will be compared to the referent group. The balance between exposure groups will be assessed overall and within each data source. If the groups are unbalanced on key covariates after application of overlap weighting, then the logistic regression model will be revised by

^{*} Overlap weighting was chosen due to the versatility of the methodology. While the method has been subject to simulations and has been used in practice, further testing is underway. If concerns about this methodology arise due to articles published while this study is underway, then inverse probability treatment weighting (IPTW) will be used as the weighting method. If this occurs, IUD insertions will be excluded when there are no comparable patients in one group versus the other (i.e., nonoverlapping propensity scores in the upper and lower tails of the propensity score distribution); patients with propensity scores close to that boundary will be excluded from further analysis. Weighting will then be based on the inverse probability of treatment, and extreme weights (e.g., $> 10^4$) will be excluded (Kurth et al., 2006; Sturmer et al., 2010). This process is called “trimming” and may affect one group more than the other. From the weighted analysis, the average treatment effect within each exposure group will be obtained (Austin, 2013; Austin, 2014). If the exposed and unexposed groups are unbalanced after trimming and application of IPTW, then the logistic regression model will be revised by including interaction terms or higher order terms, and the covariate balance between the two groups will be re-evaluated based on the revised model (Austin, 2011; Rosenbaum and Rubin, 1984).

including interaction terms (e.g., with data source), higher order terms, or transformation of variables, and the covariate balance between the groups overall and within each data source will be re-evaluated based on the revised model (Austin, 2011; Rosenbaum and Rubin, 1984). When satisfactory balance between the exposed and unexposed groups is achieved (e.g., standardized difference < 0.1), the weighting will be incorporated in modeling for confounder-adjusted outcome assessments (Section 9.7.1.3.3). If satisfactory balance is difficult to achieve, especially if there are disparate allocation percentages between groups, matching of patients between groups may be considered.

